5.1.2 Treatment Regimen

Both arms: A physician researcher will order the trial drug. The research pharmacy will dispense cannabidiol (Epidiolex) versus placebo in a securely capped amber dosing syringe packaged in bubble wrap. The dose will be made available for pick-up or mailed. The Treatment Day will either occur on or off campus. Irrespective of the study arm to which the patient is assigned, the research team will ask study participants to refrain from consuming high-calorie or -fat meals for

one hour before and after study agent consumption. Examples of foods to avoid include those high in butter, cream, oil, cheese, whole milk, mayonnaise, salad dressing, jam, syrup, honey, nuts, as well as soft drinks, juices, sweets or desserts, pastas, breads, crackers, chips and meats. Reported adverse events and potential risks are described in Section 7. Below outline specifies associated with individual arm.

Cannabidiol (Epidiolex) arm: Cannabidiol (Epidiolex) is an FDA-approved commercially-available oral solution that will be self-administered once in a 400 mg (4 mL) dose. The study drug will be consumed within 5 minutes or less. There will be no observation period post dosing. No dose modifications will be necessary. Another dose will not be administered if the participants vomits after dosing.

Placebo arm: The Dana-Farber Research Pharmacy will create the following non-sterile placebo formulation: Karo Light Corn Syrup and FLAVORx strawberry cream flavoring in a ratio 20 ml:7 drops. Karo Light Corn Syrup consists of corn syrup, salt, vanilla extract (vanilla beans, water, ethyl alcohol). The strawberry cream flavoring is dye-free and safe for the following allergies: milk, egg, soybeans, peanuts, tree nuts, wheat, grain, fish, shellfish, seeds, latex and some dyes. A 4 mL dose of placebo will be self-administered once. The study drug will be consumed within 5 minutes or less. There will be no observation period post dosing. No dose modifications will be necessary. Another dose will not be administered if the participants vomits after dosing.

Regimen Description					
Agent	Premedications; Precautions	Single Dose	Route	Schedule	Cycle Length
cannabidiol (Epidiolex) 100mg/mL	None	400 mg (4 mL; since Epidiolex's concentration is 100mg/mL)	PO	Timepoint 1	Within 48 hours of CT or PET scan
Placebo	None	400 mg (4 mL)	PO	Timepoint 1	

5.1.3 Instruments measuring study outcomes:

Demographic questionnaire (Baseline):

Variables of interest will be obtained via self-report and include: age, ethnicity, race, marital status, education, and occupational status.

Cannabis History Questionnaire (Baseline):

Cannabis use history will be obtained via self-report.

Generalized Anxiety Disorder- 7 (GAD-7) (Baseline, Timepoint 1): The widely used and validated GAD-7 measures anxiety severity on a 4-point Likert-type scale from not at all to

nearly every day. The presence of baseline anxiety, as measure by a GAD-7 score >4 , is necessary for inclusion in this study.

Patient Health Questionnaire (PHQ-9) (Baseline, Timepoint 1): The widely used and validated PHQ-9 is a 9-item depression severity measure, with scores ranging from 0 to 27. Patients are asked to rate how they felt over the past two weeks using a 4-point Likert scale. Given that anxiety and depression are closely intertwined, this measure will help us to demonstrate that the active drug and placebo arms manifest similar levels of dysphoric distress. This measure will also help in screening to rule out “uncontrolled mental illness.”

VAMS (Timepoint 1, and Timepoint 2): The Visual Analog Mood Scale (VAMS) a validated in-the-moment measure of eight specific mood states: Afraid, Confused, Sad, Angry, Energetic, Tired, Happy, and Tense. Each scale consists of a 100 mm vertical line connecting a neutral face and a face displaying a particular mood state (with an accompanying descriptor). Subjects are asked to mark their mood along this continuum. The measure is scored using a metric ruler and the “Afraid” subscale will serve as our primary endpoint. Other subscales will serve as exploratory endpoints.

EORTC-QLQc30-nausea (Timepoint 1, and Timepoint 2): The EORTC-QLQc30-nausea is a widely used and validated measure of symptom burden. It consists of 30-items, the first 28 of which employ a four-point scale (the final two are measured along a seven-point scale). Single item measures range in score from 0 to 100, with higher scores representing lower symptom burden. For the purposes of this study we will administer two items from the EORTC-QLQc30 on nausea and vomiting to assess a secondary endpoint.

Numeric Pain Rating Scale (Baseline, Timepoint 1, Timepoint 2): This widely used in-the-moment pain intensity scale is scored from 0 to 10 (with 10 representing “worst possible” pain). The NPRS will again help us to assess secondary endpoints.

Medical Record Review (Baseline, Timepoint 3): A member of the study team will record clinical data, including cancer diagnosis, disease stage, histology, and cancer treatments. Comorbidities or current medical history will also be extracted from medical records.

5.2.Pre-Treatment Criteria

5.2.1. Participants must have normal hepatic function at baseline as outlined below:

- total bilirubin	≤ 2 times institutional upper limit of normal (ULN)
- AST(SGOT)/ALT(SGPT)	$\leq 3 \times$ institutional ULN
- GAD-7 ≥ 5	

5.2.2. Cycle 1, Day 1

- Karnofsky $\geq 60\%$.

5.2.3. Subsequent Cycles

None

5.3. Agent Administration

Administration: Cannabidiol (Epidiolex), which comes in liquid form, is Federal Drug Administration-approved for rare forms of pediatric epilepsy. We will use an oral dose of 400 mg (4 mL) and will use this drug off-label for anxiety in adults with cancer. Dose administration is well within the recommended daily dose per package insert.

Dosing – This is a single dose study, with a dose of 400 mg (4 mL). Dose will be consumed within 5 minutes or less. Another dose will not be administered if the participants vomits after dosing. There will be no observation period post dosing.

Special Equipment – Disposable 10mL oral syringe with secured cap will be dispensed and either picked up, shipped, or delivered to the patient. The patient will then self-administer the cannabidiol (Epidiolex) using the oral syringe.

Oral Agents – Participants will be advised to avoid consuming high fat meals for one hour before and after study drug consumption. Examples of foods to avoid include those high in butter, cream, oil, cheese, whole milk, mayonnaise, salad dressing, jam, syrup, honey, nuts, as well as soft drinks, juices, sweets or desserts, pastas, breads, crackers, chips and meats. No other protocol specific procedures are necessary.

Caregiver Precautions – Study participants should not operate heavy machinery for 12 hours post study drug consumption.

5.3.1. CTEP and/or CIP IND Agent(s), or other IND agent

None

5.3.2. Other Agent(s)Placebo

Administration: The Dana-Farber Research Pharmacy will create the following non-sterile placebo liquid formulation: Karo Light Corn Syrup and FLAVORx strawberry cream flavoring in a ratio 20 ml:7 drops. We will use an oral dose of 4 mL.

Dosing – This is a single dose study, with a dose of 400 mg (4 mL). Dose will be consumed within 5 minutes or less. Another dose will not be administered if the participants vomits after dosing. There will be no observation period post dosing.

Special Equipment – A disposable 10mL oral syringe with secured cap will be dispensed and either picked up, shipped or delivered to the patient. The patient will then self-administer the placebo using the oral syringe.

Oral Agents – Participants will be advised to avoid consuming high fat meals for 1 hour before and after study drug consumption. Examples of foods to avoid include those high in butter, cream, oil, cheese, whole milk, mayonnaise, salad dressing, jam, syrup, honey, nuts, as well as

soft drinks, juices, sweets or desserts, pastas, breads, crackers, chips and meats. No other protocol specific procedures are necessary.

Caregiver Precautions – Study participants should not drive or operate machinery for 12 hours post study drug consumption.

5.3.3. Other Modality(ies) or Procedures

N/A

5.4. General Concomitant Medication and Supportive Care Guidelines

Because there is a potential for interaction of cannabidiol (Epidiolex) with other concomitantly administered drugs through the cytochrome P450 system, a licensed physician on the study team will review participants list of medication prior to study drug administration.

5.5. Criteria for Taking a Participant Off Protocol Therapy

The planned duration of therapy is a single day. Treatment will be halted in the setting of:

- Inability to ingest study medication on the day of study
- Intercurrent illness that prevents administration of treatment
- Unacceptable adverse event(s)
- Participant demonstrates an inability or unwillingness to comply with the oral medication regimen and/or documentation requirements
- Participant decides to withdraw from the protocol therapy
- General or specific changes in the participant's condition render the participant unacceptable for treatment in the judgment of the treating investigator

Participants will be removed from the protocol therapy when any of these criteria apply. The reason for removal from protocol therapy, and the date the participant was removed, must be documented in the case report form (CRF). Alternative care options will be discussed with the participant.

When a participant is removed from protocol therapy and/or is off of the study, the participant's status must be updated in OnCore in accordance with [REGIST-OP-1](#).

5.6. Duration of Follow Up

Participants will be followed for *approximately 1 week* after removal from protocol therapy or until death, whichever occurs first. Participants removed from protocol therapy for unacceptable adverse event(s) will be followed until resolution or stabilization of the adverse event.

5.7. Criteria for Taking a Participant Off Study

Participants will be removed from study when any of the following criteria apply:

- Lost to follow-up
- Withdrawal of consent for data submission
- Death
- Investigators discretion

The reason for taking a participant off study, and the date the participant was removed, must be documented in the case report form (CRF). In addition, the study team will ensure the participant's status is updated in OnCore in accordance with [REGIST-OP-1](#).

There will also be a protocol around emergency unblinding. In this double-blind study, the research pharmacy not be blinded. Unblinding will occur when knowledge of the treatment is essential for the emergency management of a serious adverse event (SAE) as defined in section 7.1. Unblinding of the study for other reasons will be considered a major protocol violation. The PI must be notified if unblinding of a patient is necessary. The PI has designated the responsibility of unblinding to the MD's only. MD requesting this will notify and discuss with PI either by phone or email and when approved by the PI, the treating MD will notify the research pharmacy. An email will be sent to the research pharmacy at [contact] with the protocol number, the patient name, MRN, the reason for the unblinding, and indicating the PI's approval. The DFCI research pharmacy will send the unblinded information back to the MD and receipt of the email will be acknowledged by the MD. During off hours, weekends, and holidays, the pharmacy administrator on call will be paged via the DFCI page operator at [contact] from within DFCI, or [contact] from outside DFCI.

6. DOSING DELAYS/DOSE MODIFICATIONS

This is a single dose study, therefore dosing delays are not allowed or applicable. There will be no modifications to the dose of cannabidiol (Epidiolex) or placebo given to study participants. Although there are recommended dose adjustments in individuals with hepatic dysfunction, these individuals are excluded from the study.

7. ADVERSE EVENTS: LIST AND REPORTING REQUIREMENTS

Adverse event (AE) monitoring and reporting is a routine part of every clinical trial. The following list of reported and/or potential AEs (Section 7.1) and the characteristics of an observed AE (Section 7.2) will determine whether the event requires expedited reporting **in addition** to routine reporting. Because this study is being completed in an advanced illness population, deaths due to cancer are expected. The research team will not report cancer-related deaths as adverse events.

The principal investigator will be responsible for monitoring and reporting all adverse events to the DFCI IRB for this study, but in the event that the principal investigator is unavailable, the co-investigators will assume this responsibility. The role of the responsible person is to 1) identify the concern, 2) develop the appropriate response to the concern with the use of consultants if necessary and 3) ensure proper reporting of concerns to the IRB.

All potential adverse events will be reported to the PI. The PI in consultation with Co-investigators will classify events according to level of severity. Details will be recorded on an adverse case report form as well as logged on a secure spreadsheet for reporting to the IRB.

The adverse event case report form will include a description of all undesirable experiences, required interventions, and an assessment of the subject after the event if possible. An estimate of the extent of injury, and prevention strategies will be reported. The principal investigator will classify the relationship of the study protocol to the event as follows:

- Not related: The event is clearly related to factors such as the subject's clinical state, not with the study protocol.
- Remote: The event was most likely related to factors such as the subject's clinical state, not with the study protocol.
- Possible: The event follows a reasonable temporal sequence associated with participating in the study and/or is consistent with events related to responding to queries about stress/drug craving but is possibly related to factors such as the subject's clinical state.
- Probable: The event follows a reasonable temporal sequence associated with participating in the study and/or is consistent with events related to dosing of cannabidiol (Epidiolex) in the study and cannot be reasonably explained by factors such as the subject's clinical state. The severity of an adverse event in both groups is defined as a qualitative assessment of the degree or intensity of an adverse event as determined by the principal investigator as follows:
 - Mild: No impact (in anyway) on the subjects.
 - Moderate: Impacts on the subject but is not life-threatening or incapacitating.
 - Severe: Fatal, life threatening, permanently disabling; severely incapacitating; requires/prolongs inpatient hospitalization.

7.1. Expected Toxicities

7.1.1. Adverse Events List(s) for cannabidiol (Epidiolex)

The most likely adverse event from single dose cannabidiol (Epidiolex) in this investigation is somnolence. Although we will ask study participants to refrain from benzodiazepine use between study visits 2 and 3, participants may still use benzodiazepines while not under the study team supervision. Combination of benzodiazepine plus cannabidiol (Epidiolex) may result in somnolence. No reports of hypopnea or respiratory arrest have been described with cannabidiol (Epidiolex). Please refer to attached commercial package insert for details and comprehensive list of adverse events. They include:

- nonfatal hepatotoxicity
- seizures
- suicidal ideation or behavior
- nausea and vomiting

7.1.2. Adverse Events List(s) for Placebo

- none

7.1.3. Adverse Events List(s) for PHQ-9

- Any participant who evidences potential suicidal ideation on the PHQ-9 will be evaluated by one of the study's psychiatrists or referred a psycho-oncologist in the Department of Psychosocial Oncology and Palliative Care for such clinical evaluation.

7.2. Adverse Event Characteristics

- **CTCAE term (AE description) and grade:** The descriptions and grading scales found in the revised NCI Common Terminology Criteria for Adverse Events (CTCAE) version 5.0 will be utilized for AE reporting. All appropriate treatment areas should have access to a copy of the CTCAE version 5.0. A copy of the CTCAE version 5.0 can be downloaded from the CTEP web site http://ctep.cancer.gov/protocolDevelopment/electronic_applications/ctc.htm.
- **For expedited reporting purposes only:**
 - AEs for the agent(s) that are listed above should be reported only if the adverse event varies in nature, intensity or frequency from the expected toxicity information which is provided.
 - Other AEs for the protocol that do not require expedited reporting are outlined in the next section (Expedited Adverse Event Reporting) under the sub-heading of Protocol-Specific Expedited Adverse Event Reporting Exclusions.
- **Attribution of the AE:**
 - Definite – The AE is *clearly related* to the study treatment.
 - Probable – The AE is *likely related* to the study treatment.
 - Possible – The AE *may be related* to the study treatment.
 - Unlikely – The AE is *doubtfully related* to the study treatment.
 - Unrelated – The AE is *clearly NOT related* to the study treatment.

7.3. Adverse Event Reporting

- 7.3.1. In the event of an unanticipated problem or life-threatening complications treating investigators must immediately notify the Overall PI.
- 7.3.2. Investigators **must** report to the Overall PI any adverse event (AE) that occurs after the single dose of study drug, or within 30 days of the single dose of study drug on the local institutional SAE form.

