Timepoint 1 (Pre-drug Administration): Regardless of randomization arm, all participants will complete a set of questionnaires. The study team will review questionnaire responses assessing cannabis and benzodiazepine uses (e.g. section 3.1.8 & 3.1.9 of the eligibility criteria). If a participant indicates they have consumed either within the prohibited timeframe, the study team will attempt to delay study drug administration in order to meet eligibility criteria. (Section 5 offers full details on consuming study drug). However, if the study drug administration cannot be delayed, the Treatment Day will be rescheduled to coincide with the next scheduled CT scan or positron emission tomography (PET). See section 8.1.11. for unused study drug destruction.

Timepoint 2 (Post-drug Administration): All participants will complete a set of questionnaires.

Timepoint 3: Study staff will phone the participant within a week +/- 7 days of study drug consumption to conduct a brief, semi-structured audio-recorded interview.

At study completion participants will receive a \$50 gift card. They will also receive up to \$50 for qualifying study-related travel costs and/or expenses. After all study procedures are completed, the research team will contact participants to inform of which arm they were assigned after unblinding and share any publications that come from this study.

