9. STUDY CALENDAR

	Baseline assessment	Timepoint 1 Treatment day, pre-assessment	Timepoint 2 Treatment day, post-assessment	Timepoint 3 Follow-up assessment
	Prior to Timepoint 1	Within 48 hours of a CT/PET scan to assess tumor burden	3 (+/- 1) hour post ingestion	<1-week (+/- 7 days) post ingestion
Background Information				
Informed consent***	X			
Screener questionnaire	X			
Demographics	X			
Medical history	X			X
Concurrent medications	X	X		
Performance status	X			
LFTs	X			
bHCG**	X			
GAD-7	X	X		
PHQ9	X	X		
Cannabis History Questionnaire	X			
Cannabidiol (Epidiolex) vs. Placebo		X*		
Confirmation of study drug consumption				
Patient Provisions				
\$50 gift card				X
Primary endpoints				
VAMS afraid subscale		X	X	
Secondary endpoints				
NPRS	X	X	X	
EORTC-QLC30-nausea		X	X	
Other subscales of VAMS		X	X	
Qualitative interview				X
Safety Monitoring				
Adverse Event Evaluation		X	X	

* = Study drug to be administered after completion of Treatment day, pre-assessments

**= bHCGs will be collected on all potential participants under the age of 54-years, unless known to be post-menopausal or status post hysterectomy

*** = to be completed with physician involvement

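### Adverse events are reportable for 30 days after the single dose, but follow-up ends at about 1 week and no adverse-event ascertainment is scheduled after Timepoint 3, which may fall anywhere from day 0 to day 14

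*Combined protocol and SAP*

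**What the plan says.** Four places in the combined protocol and SAP bear on how long adverse events (AEs) are looked for.

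- **Section 7.3.2** sets the reporting duty: "any adverse event (AE) that occurs after the single dose of study drug, or within 30 days of the single dose of study drug". Reports go to the Overall PI on the institutional SAE form.
- **Section 5.6** sets follow-up: "Participants will be followed for *approximately 1 week* after removal from protocol therapy", or until death if sooner. Section 5.5 adds: "The planned duration of therapy is a single day". The only extension is for participants taken off therapy because of an unacceptable AE, who are followed until that event resolves or stabilises.
- **Section 5.1.1** sets the last contact, Timepoint 3: "Study staff will phone the participant within a week +/- 7 days of study drug consumption". It is a short, semi-structured, recorded interview. The study calendar (Section 9) heads the same column "1-week (+/- 7 days) post ingestion".
- **The study calendar** has a row for "Adverse Event Evaluation". As extracted, its two marks fall under Timepoints 1 and 2, both on the treatment day, with none under Timepoint 3.

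Section 5.1.3 also places a medical record review at Timepoint 3. It lists diagnosis, stage, histology, cancer treatments and comorbidities, and does not name AEs. Section 5.3 says "There will be no observation period post dosing". Section 11.7.1 makes participants evaluable for toxicity from first treatment and gives no end date.

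**The concern.** The reporting period, the end of follow-up and the last contact do not agree. A 30-day reporting period suggests that events up to day 30 will be known about, yet participants leave follow-up at about day 7 and no call, visit, survey or chart review is planned after Timepoint 3. Under that schedule, an absence of reported late events would partly mean that nobody asked.

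The Timepoint 3 window adds a second problem. With a tolerance equal to its interval, the call could be made on the dosing day or a week after Section 5.6 has closed follow-up. Two patients treated alike could therefore have quite different lengths of planned observation.

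At stake is the completeness and comparability of the AE data. Side effects are a secondary objective (Section 1.2), and better assessment of them is one of the two reasons given for 2:1 randomisation (Section 11.1).

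**Working it through.** The plan states no figure of its own to reproduce. The check is date arithmetic, counting the dosing day as day 0.

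**Inputs**
- Reporting period: 30 days (Section 7.3.2). The first half of that sentence, read alone, has no end; I take 30 days as the intended limit.
- End of follow-up: one day of therapy (5.5) plus about 1 week (5.6), so about day 7.
- Timepoint 3: one week with a tolerance of 7 days (5.1.1 and calendar).

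**Timepoint 3 window.** Earliest: 7 − 7 = day 0. Latest: 7 + 7 = day 14. Taking the target as up to one week, rather than exactly day 7, gives the same limits.

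**Days with nothing scheduled.** Formula: (30 − day of Timepoint 3) / 30.

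| Timepoint 3 on | Days left of 30 | Share |
|---|---|---|
| Day 14 (latest allowed) | 30 − 14 = 16 | 53% |
| Day 7 (nominal) | 30 − 7 = 23 | 77% |
| Day 0 (earliest, literal) | 30 − 0 = 30 | 100% |

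**Spread between patients.** 14 − 0 = up to 14 days of difference in planned ascertainment time.

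**Agreement with Section 5.6.** A call on day 14 comes 14 − 7 = 7 days after follow-up has nominally ended.

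The table credits the Timepoint 3 call with ascertaining AEs up to its date. The documents do not say that it does: the chart review does not name AEs, and the calendar as extracted has no AE mark there. Section 1.2 pairs the PRO-CTCAE with a qualitative assessment of side effects, so the interview probably touches on them. The 53% and 77% are therefore lower bounds on the gap for their respective call dates.

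**The case against.** The strongest reply is that Sections 7.3.2 and 5.6 govern different things. The first says for how long an event that becomes known must be reported; the second says how long participants are actively followed. A reporting duty can outlast scheduled visits, and both sentences can be obeyed as written. Participants are identified from the centre's own breast oncology and imaging schedules, so late events may well reach investigators. This stands: a reader might infer that most of the 30 days is unobserved, but the documents support only that it has no scheduled ascertainment.

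A reader might also infer that a 30-day safety table would mislead. No such table is planned. Section 11 tables the PRO-CTCAE profile by side effect, without tying it to the 30-day investigator reports.

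Nor is between-arm bias shown. Both blinded arms share the same Timepoint 3 window, and the primary endpoint is measured about 3 hours after dosing.

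The day-0 case is a literal extreme, since Timepoint 3 is labelled a follow-up assessment. A late call is the more realistic problem.

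Finally, one might infer from the calendar that formal AE evaluation stops 2 to 4 hours after dosing. That rests on column positions in text extracted from a PDF, so I do not rely on it.

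What the reply leaves untouched is that passive capture is not systematic. The extension in Section 5.6 tracks a known event in a participant already taken off therapy; it does not detect new ones.

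**Conclusion.** The concern holds in a limited form. The plan sets a 30-day AE reporting period that its schedule cannot systematically fill. At least 16 of the 30 days (53%) follow the last scheduled contact, rising to 23 (77%) with the call on day 7, and planned ascertainment can differ between patients by up to 14 days.

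This assumes that 30 days is the intended limit, that the Timepoint 3 window is applied as written, and that the call counts as AE ascertainment. If the call does not count, the gap is larger.

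The effect is on the completeness and uniformity of the AE data. This is a minor point: worth correcting, but no threat to the main comparison.

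**What to change.** Reconcile Sections 5.6 and 7.3.2, the Timepoint 3 text in 5.1.1 and the study calendar:

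1. Add an explicit AE query to the existing Timepoint 3 call and mark it in the calendar.
2. Give Timepoint 3 a window that excludes the dosing day and agrees with Section 5.6.
3. Choose one AE period. Either keep 30 days, extend 5.6 to match and add a day-30 chart check that explicitly extracts AEs; or restate the period in 7.3.2 to the follow-up actually planned. Moving the present Timepoint 3 record review to day 30 would not be enough, because its listed content does not include AEs.
4. State in Section 11 that investigator-reported AEs will be summarised over that one common period in both arms.

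The cost is protocol wording and one added question set in a call already planned. Beyond that, the first option needs about 50 brief chart checks, one per randomised patient; the second gives a shorter safety claim.
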